#### 7.1.2 Pegloticase

[REDACTED]

Two replicate pivotal Phase 3 studies for pegloticase were undertaken to establish the efficacy and safety of the product. The primary endpoint was defined as plasma uric acid (pUA) (highly correlated to serum uric acid) reduction to below 6 mg/dL for 80% of the time in Months 3 and 6 combined. The pooled response rate for pegloticase 8 mg every two weeks was 42%, versus a placebo response rate of 0%. There was also a greater reduction in complete resolution of  $\geq 1$  tophus in the every 2 weeks dosing group, and favorable effect of pegloticase treatment in the reduction of the number of tender and swollen joints. In subsequent open-label extension studies, pegloticase led to continued control of pUA, reduction in gout flares, and continued resolution of tophi, suggesting continuing benefit with extended pegloticase treatment beyond the initial 6 months of therapy, particularly in subjects who met responder criteria in the placebo-controlled trials.

In the Phase 3 pivotal studies, deaths, AEs, SAEs, as well as laboratory abnormalities were generally equally distributed across placebo and pegloticase treatment groups, with the clear exception of gout flares and infusion reactions (IRs). Pegloticase-treated subjects exhibited a higher rate of gout flares during Months 1-3 as uric acid was being acutely lowered, then a decrease in gout flares vs. placebo during Months 4-6. Despite use of prophylactic medications against hypersensitivity including administration of corticosteroids, antihistamine, and acetaminophen in advance of each pegloticase infusion, IRs were seen in 22/85 (26%) of subjects receiving the 8 mg 2 week regimen. There was no specified definition of anaphylaxis in the Phase 3 protocols, and there were no investigator-reported events of anaphylaxis in the Phase 3 studies with pegloticase.

However, in a post-hoc review applying the National Institute of Allergy and Infectious Diseases/ Food Allergy and Anaphylaxis Network (NIAID/FAAN) criteria ([Sampson et al., 2006](#)), it was determined that across the Phase 2 and Phase 3 program, anaphylaxis occurred in 6.5% of subjects treated with pegloticase dosed every 2 weeks. Anaphylaxis generally occurred within 2 hours after treatment. Manifestations included wheezing, peri-oral or lingual edema, or hemodynamic instability, with or without rash or urticaria. All of these events had relatively rapid resolution with the cessation of infusion.

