In a post-hoc analysis, the apparent role of immunogenicity in both loss of urate lowering effect and incidence of IRs was appreciated. Only 2% of subjects with anti-pegloticase antibody titers exceeding 1:2430 maintained a urate-lowering response to pegloticase compared with 63% of subjects who were treated for at least 2 months without developing high-titer antibodies ( $p < 0.001$ ) ([Sundy et al., 2011](#)). The incidence of IRs was higher among subjects who developed high-titer antibodies compared with those who had titers that did not exceed 1:2430 (60% vs. 19%;  $p < 0.001$ ) ([Sundy et al., 2011](#)). In addition, most IRs occurred when sUA levels were greater than 6 mg/dL. Retrospective analyses showed that the loss of urate-lowering efficacy, as reflected by sUA of greater than 6 mg/dL, preceded a patient's first IR, whenever it occurred, in 20 (91%) of 22 subjects treated with pegloticase every 2 weeks.

Therefore, discontinuation of pegloticase therapy in subjects who lose urate-lowering response offers a valuable approach for mitigating the risk of IR. A post-hoc analysis of the biweekly pegloticase dosing group in the randomized controlled trials (RCTs) illustrated the impact of several possible stopping rules based on sUA levels. A stopping rule based on 2 consecutive pre-infusion sUA

measurements of greater than 6 mg/dL would have significantly reduced the risk of IR (from 26% to 8%), while having little effect on the treatment response rate (from 42% to 41%) (Keenan et al., 2019). Early post-approval safety surveillance in the US using the stopping rules demonstrated a 69% reduction in the rate of IRs compared with the IR rate recorded during the RCTs (Malamet et al., 2013).

Reducing anti-drug antibodies (ADA) with concomitant administration of the immunomodulatory agent methotrexate (MTX) has been shown to be useful with other infused products that lead to immunogenicity, such as infliximab, in the setting of rheumatoid arthritis treatment. In a recent, prospective, proof-of-concept case series, nine patients with refractory tophaceous gout were pre-treated with MTX prior to co-administration of MTX with KRYSTEXXA. All nine patients were responders as defined by maintaining a serum uric acid at goal of <6 mg/dL for greater than 80% of the observation period, which ranged from 4.5 to

9 months on therapy. No unexpected adverse effects were reported with this coadministration (Botson and Peterson, 2018).

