## 9.2 Discussion of Study Design

This is a Phase 4, multi-site, open-label, single arm study to assess efficacy and safety of pegloticase in adult subjects with uncontrolled gout who have undergone kidney transplantation.

During the pre-marketing Phase 3 studies for pegloticase, subjects with organ transplant were excluded from participation; however, subjects with renal impairment were included, and showed comparable safety and efficacy as the general study population. Kidney transplant recipients with uncontrolled gout have the potential to benefit from the ability of pegloticase to rapidly deplete urate deposits, even when urate excretion is impaired. In addition, immunosuppressive agents to prevent rejections have the potential to thwart the formation of ADA against pegloticase, thereby preserving its effectiveness and decreasing the risk of infusion reactions.

This study will test safety and effectiveness of pegloticase (administered 8 mg via IV infusion every 2 weeks, consistent with the current pegloticase prescribing information) in kidney transplant subjects with chronic gout refractory to conventional urate lowering therapy.

Prospective use of sUA stopping rules, with pegloticase treatment cessation (but study continuation) when a subject has a pre-infusion sUA level >6 mg/dL on two consecutive study visits, will also help confirm the value of this approach to reduce IR risk.

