##### 9.6.5.1 Primary and Secondary Endpoint Analysis

The primary efficacy endpoint is the proportion of responders during Month 6. A responder is defined as a subject for whom the proportion of time that the sUA-time curve is  $<6$  mg/dL during the analysis interval is at least 80%. The proportion of time that the sUA level is below 6 mg/dL is defined as the ratio of the time during which the sUA level remains below 6 mg/dL (using linear interpolation, if necessary) to the entire time interval during Month 6. The proportion of responders will be summarized, along with a 95% exact (Clopper-Pearson) confidence interval (CI) for the proportion.

A subject will be declared a non-responder if the subject had 2 pre-infusion sUA levels  $>6$  mg/dL at 2 consecutive study visits beginning with the Week 2 Visit and prior to or during Month 6. Additionally, a subject who withdraws from study treatment for any reason other than the stopping rule after the first dose of pegloticase and prior to or during Month 6 will be considered a non-responder if sUA values are not collected at planned timepoints. Special consideration may be given to subjects who discontinue the study or miss visits due to reasons related to the COVID-19 pandemic.

The mean change from baseline to each visit in HAQ pain score and HAQ-DI score will be summarized with descriptive statistics, including 95% CIs for the change from baseline.

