### 9.6.7 Safety Analysis

Treatment-emergent AEs are defined as events with an onset date on or after the start of the first pegloticase infusion through 30 days after the last dose of pegloticase. AEs that occur more than 30 days after the last dose of pegloticase through the 3-month follow-up visit will also be summarized.

The number and percentage of subjects experiencing AEs will be summarized by system organ class and preferred term. Summaries by maximum severity and relationship to study drug will also be provided. SAEs and AEs leading to discontinuation of study drug will be presented by system organ class and preferred term. The proportion of subjects with each AESI will also be summarized.

Laboratory test results will be summarized by study visit and change from baseline. Shift tables for laboratory parameters by Common Terminology Criteria for Adverse Events grade will be presented. Laboratory test results will also be classified relative to the normal reference range (normal, low, or high).

Vital signs, including BP, respiratory rate, temperature, and heart rate, will be summarized by study visit and change from baseline.

Prior and concomitant medications will be summarized and/or included in the data listings.

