### 9.6.9 Sample Size and Power Considerations

A sample size of 20 subjects is planned for this study. The primary efficacy endpoint, the proportion of subjects achieving and maintaining sUA <6 mg/dL for at least 80% of the time during Month 6, will be demonstrated to be statistically greater than 43.5% (proportion of responders during Month 6 in the Phase 3 studies), if at least 14/20 (70%) responders are observed. In that case, the lower bound of a 95% confidence interval for the proportion of responders will be about 46%.

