The proportion of hours during the period during which the sUA was less than 6 mg/dL will be summarized using descriptive statistics. If a subject has  $\leq 1$  data point in the period, then the proportion of hours will not be calculated. The number and proportion of subjects that discontinued treatment due to the stopping rule will be summarized. The number and proportion of responders will be summarized along with a 95% exact (Clopper-Pearson) CI for the proportion. In addition, the number and proportion of subjects missing all data in analysis period, subjects with only one measurement (above cutoff) in analysis period, and subjects with only one measurement (below cutoff) in analysis period will be summarized.

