3. Reduced blood pressure after exposure to known allergen for that subject (minutes to several hours): systolic blood pressure  $<90$  mmHg or  $>30\%$  decrease from that subject's baseline.

The signs and symptoms associated with each event are entered on the eCRF and will be coded to the MedDRA dictionary.

Summaries of IRs and anaphylaxis will group events by 3 categories:

- Anaphylaxis
- Infusion reactions including anaphylaxis
- Infusion reactions excluding anaphylaxis

Both the investigator-reported and adjudicated events and the associated signs and symptoms, will be summarized separately by SOC, PT, severity, and the time relative to the most recent pegloticase infusion for each category above.

Time relative to the most recent pegloticase infusion will be categorized as: during infusion,  $\leq 2$  hours after infusion,  $> 2$  hours to 24 hours after infusion, and  $> 24$  hours after infusion. If the time of the infusion reaction or anaphylaxis is missing, the category will be assigned as "Missing".

This document is confidential.

Serious events and the associated symptoms will be summarized by SOC and PT for each category.

The number of events per subject, the number of events and serious events per infusion, and the number of subjects with the first event by infusion number will be summarized as well for each category. IRs (including anaphylaxis) that occur on the same date will be considered one event.

Time to first infusion reaction or anaphylaxis (Kaplan-Meier analysis) will be plotted. Time to first infusion reaction or anaphylaxis for subjects who experience infusion reaction or anaphylaxis (continuous variable descriptive stats) will be summarized. Summaries of events will be tabulated only if 5 or more subjects have either an event adjudicated as an IR or anaphylaxis or any events in the database identified as IRs or anaphylaxis.

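### No confidence interval is planned for adverse events of special interest, although the infusion-reaction rate is meant to bear on the stopping rule; with 20 subjects, 2 to 4 reactions fit both quoted benchmarks (8% and 26%)

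*Protocol*

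**What the plan says.** AESI incidence (infusion reactions, anaphylaxis, gout flares, cardiovascular events) is a named safety endpoint in Protocol 9.6.1.5 and SAP 5.5.

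- **Protocol 9.6.7:** "The proportion of subjects with each AESI will also be summarized". No interval is mentioned.
- **SAP 12.3.2:** numbers and percentages of subjects, numbers of events and, on most tables, incidence per person-year of exposure. The overall table has one combined line for AESIs.
- **SAP 12.3.3.1:** infusion reactions and anaphylaxis by category, severity and timing, both investigator-reported and adjudicated. It adds "The number of events per subject, the number of events and serious events per infusion, and the number of subjects with the first event" (the last of these broken down according to which infusion it was), and a Kaplan-Meier plot of time to first event. No interval is stated. Summaries are tabulated only if 5 or more subjects have an event; SAP 12.3.3.2 sets the same threshold for cardiovascular events.
- **Efficacy, for contrast:** Protocol 9.6.5.1 has "The proportion of responders will be summarized, along with a 95% exact (Clopper-Pearson) confidence interval (CI) for the proportion", and SAP 10.2 has "The number and proportion of responders will be summarized along with a 95% exact (Clopper-Pearson) CI for the proportion". SAP 10.3.1 applies the same method to the 5 mg/dL responders. The protocol synopsis plans a 95% interval for tophus resolution.
- **Benchmarks, Protocol 7.1.2:** "IRs were seen in 22/85 (26%) of subjects receiving the 8 mg 2 week regimen". A post-hoc analysis there puts the rate at 8% had the stopping rule been applied, and anaphylaxis at 6.5%.
- **Stated use of the result, Protocol 9.2 (also 7.2):** prospective use of the stopping rule "will also help confirm the value of this approach to reduce IR risk".

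**The concern.** A single-arm study has no concurrent group without the stopping rule. It can help confirm that the rule lowers infusion-reaction risk only by setting its own rate beside the historical ones. For efficacy the protocol handles that kind of comparison properly: section 9.6.9 compares the lower confidence limit for 14/20 responders with a historical 43.5%. For infusion reactions it quotes benchmarks and states a purpose, but plans no measure of precision.

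At stake is how a moderately low count is read. A result such as 2/20 (10%) sits close to 8% and well under 26%, so it invites the conclusion that the rule works, when the data do not separate the two rates. Likewise 0/20 anaphylaxis invites the conclusion that the risk is absent. The 5-subject threshold adds to this: the counts that would count as favourable are those for which the dedicated tables are not produced.

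**Working it through.** **Inputs.** Planned size (Protocol 9.6.9): "A sample size of 20 subjects is planned for this study"; COVID-19 replacements may raise this. Benchmarks from Protocol 7.1.2: 22/85 = 25.9% (26%), 8%, and 6.5% for anaphylaxis. Interval method from SAP 10.2: two-sided 95% Clopper-Pearson.

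**Formula.** For x events in n subjects, the lower limit is the 0.025 quantile of Beta(x, n−x+1) and the upper limit is the 0.975 quantile of Beta(x+1, n−x). For x = 0 the lower limit is 0.

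**Step 1: reproduce the plan's own figure.** For 14/20 the limits are 45.7% and 88.1%. The lower limit matches the stated figure of about 46%. For 13/20 it is 40.8%, below 43.5%, so 14 is the minimum count, as the protocol says.

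**Step 2: apply the same interval to infusion reactions, n = 20.**

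| Subjects with a reaction | Observed | Exact 95% interval | Contains 8%? | Contains 26%? |
|---|---|---|---|---|
| 0 | 0% | 0 to 16.8% | yes | no |
| 1 | 5% | 0.1 to 24.9% | yes | no |
| 2 | 10% | 1.2 to 31.7% | yes | yes |
| 3 | 15% | 3.2 to 37.9% | yes | yes |
| 4 | 20% | 5.7 to 43.7% | yes | yes |
| 5 | 25% | 8.7 to 49.1% | no | yes |

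**Step 3: how often each outcome occurs (binomial, n = 20).**

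| True rate | P(0 or 1) | P(2 to 4) | P(5 or more) |
|---|---|---|---|
| 8% | 51.7% | 46.5% | 1.8% |
| 26% | 1.9% | 35.6% | 62.5% |

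The range that fits both benchmarks is therefore common under either rate.

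**Step 4: how firm are the results at 0 and 1?** The 26% is itself an estimate: 22/85 has an exact 95% interval of 17.0% to 36.5%. Against that sample, Fisher's exact test gives p = 0.011 for 0/20 and p = 0.068 for 1/20. With one event, the upper limit is 27.3% at n = 18 and 26.0% at n = 19, so 26% is no longer excluded; at n = 22 it is 22.8% and 26% is excluded. The 0-event result is firm; the 1-event result is borderline.

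**Step 5: anaphylaxis.** At a true rate of 6.5%, P(0/20) = (1 − 0.065)^20 = 0.935^20 = 26%. The upper limit for 0/20 is 16.8%, well above 6.5%.

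**Step 6: the 5-subject threshold.** It is missed when 4 or fewer subjects have an event. P(X ≤ 4) is 51.7% + 46.5% = 98.2% at a true 8%, and 1.9% + 35.6% = 37.5% at a true 26%. This takes the threshold count to be the same as the infusion-reaction count. SAP 12.3.3.1 counts both adjudicated events and any others identified in the database, so the actual chance of missing it could be somewhat lower.

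**The case against.** Several points on the other side stand.

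- **Low counts do not all fit both benchmarks.** A reader might infer that any low infusion-reaction rate would be compatible with both 8% and 26%. The arithmetic does not support that: 0/20 and 1/20 exclude a fixed 26%, and at a true 8% one of these is the outcome about half the time.
- **The SAP offers more than bare percentages.** Person-year incidence, events per infusion and a Kaplan-Meier plot are planned. None has a stated interval, so the gap is narrower but remains.
- **Not every efficacy proportion can be shown to get an interval.** The exploratory analyses are largely redacted, and SAP 10.2 itself summarises the proportion stopped under the rule with no stated interval. The contrast holds for the responder and tophus-resolution proportions.
- **No comparison with 26%, 8% or 6.5% is written into an analysis section.** Those figures stand in the background, and Protocol 9.6.5 rules out formal testing of efficacy. It would go too far to say that the sponsor plans a claim of lower risk. But 9.6.5.1 plans intervals without tests, and Protocol 7.2 and 9.2 do give the infusion-reaction result a confirmatory purpose.
- **A reader can compute the interval from n and N.** True where the count is tabulated, but below the threshold the dedicated tables are not produced.

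One tempting remedy also fails: a rule that a rate may be called lower only if its upper limit falls below the quoted rate. It treats 22/85 as known exactly, and at n = 20 it could never be met for 6.5% or 8%, because even 0/20 reaches 16.8%. The readable documents give no historical subject-level rate for flares or cardiovascular events.

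**Conclusion.** The concern holds in limited form. No AESI proportion has a stated interval in Protocol 9.6.7 or the readable SAP 12.3, while the study is said to inform whether the stopping rule reduces infusion reactions. With 20 subjects, 2, 3 or 4 reactions would look like a reduction but would not distinguish 8% from 26%; that happens 46.5% of the time at a true 8% and 35.6% at a true 26%. Zero reactions would be real evidence against 26%; one would be weak evidence. The reporting threshold would suppress the dedicated tables in about 98% of trials at a true 8%.

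These figures assume 20 dosed subjects, independent outcomes, and one infusion-reaction status per subject. The 8% and 26% are the protocol's quoted rates, used as scenarios and not as forecasts for transplant recipients. Even an interval wholly below 26% would not isolate the stopping rule, because Protocol 9.2 also expects immunosuppression to lower the risk.

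This is an inexpensive improvement in reporting. It does not affect the primary analysis or the safety data collected.

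**What to change.** In SAP 12.3.3, add one summary that is always produced. It gives the number and proportion of dosed subjects with at least one event for each AESI, at minimum infusion reaction and anaphylaxis, with a two-sided 95% exact (Clopper-Pearson) interval as in SAP 10.2. State that the 5-subject threshold does not apply to this summary; it can stay for the detailed breakdowns.

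Add a sentence that any comparison with the historical 26%, 8% or 6.5% is descriptive, will be read with the interval, and takes into account that 26% is itself an estimate from 22/85.

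Cost: one short table and a few lines of SAP text, with no new data and no extra subjects. Downside: the safety figures will look less certain, and the table appears even when it holds only zeros.

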### 9.6.8 Interim Analyses

No formal interim analysis is planned for this study. Efficacy and safety data may be summarized after 10-15 subjects have been followed through Week 24. Additional summary of the data may be performed periodically throughout the study, and safety data will be summarized regularly for safety monitoring. Final analysis will occur when all subjects have completed the study.

### 9.6.9 Sample Size and Power Considerations

A sample size of 20 subjects is planned for this study. The primary efficacy endpoint, the proportion of subjects achieving and maintaining sUA <6 mg/dL for at least 80% of the time during Month 6, will be demonstrated to be statistically greater than 43.5% (proportion of responders during Month 6 in the Phase 3 studies), if at least 14/20 (70%) responders are observed. In that case, the lower bound of a 95% confidence interval for the proportion of responders will be about 46%.

## 9.7 Changes in the Conduct of the Study

If any modifications in the experimental design, dosages, parameters, subject selection, or any other sections of the protocol are indicated or required, the Investigator will consult with the Sponsor before any such changes are instituted. Modifications will be accomplished through formal amendments to this protocol by the Sponsor and approval from the appropriate IRB.

All protocol deviations and the reasons for such deviations **must** be documented in the eCRF. In the event of a major protocol deviation, the Investigator and Sponsor's Medical Monitor will determine whether the subject should continue to participate in the study.

The Sponsor has a legal responsibility to report fully to regulatory authorities all results of administration of investigational drugs to humans. No investigational procedures other than those described in this protocol will be undertaken on the enrolled subjects without the agreement of the IRB and Sponsor.

## 10 SOURCE DOCUMENTATION AND INVESTIGATOR FILES

The Investigator must maintain adequate and accurate records to document fully the conduct of the study and to ensure that study data can be subsequently verified. These documents should be classified in 2 separate categories: (1) Investigator study file and (2) subject clinical source documents that corroborate data collected in the eCRFs. Subject clinical source documents would include, as applicable, original hospital/clinic subject records; physicians' and nurses' notes; appointment book; original laboratory, ECG, electroencephalogram, radiology, pathology, and special assessment reports; dispensing records; signed ICFs; consultant letters; and subject screening and enrollment logs.

In order to comply with regulatory requirements, it is the policy of the Sponsor that, at a minimum, the following be documented in source documents at the study center:

- Medical history/physical condition and diagnosis of the subject before involvement in the study sufficient to verify that the subject meets protocol entry criteria;
- Study number, assigned subject number, and verification that written informed consent was obtained (each recorded in dated and signed progress notes);
- Progress notes for each subject visit (each dated and signed);
- Records of each study visit including each study assessment and the identity of the staff member performing the assessment;
- Study drug dispensing and return;
- Review by the Investigator or qualified personnel on the 1572 of laboratory test results;
- AEs (start and stop date, description, action taken, and resolution);
- Investigator or sub-investigator's signed assessment of AEs;
- Concomitant medications (start and stop dates, reason for use); and
- Condition of subject upon completion of, or premature withdrawal from, the study.

